3. STUDY DESIGN AND PROCEDURES

3.1. Overall study design and flow chart

Design: The COMB-BO8 study is a Phase II, randomized, multicentre, double-blind, placebo-controlled trial with 4 parallel groups.

[figure not shown]
Trial Time Line COMB-BO8

Figure 2. Schematic time line for study visits. The study comprises a double-blind phase with 9 visits in total over 13 weeks (91 days). Day 0-7 is titration of dosing.

The required time for study participation is shown in table 2.

Visits	Day	Estimated time for visits	
Visit 1	Baseline	Medical visit/ Scr	3hrs
Visit 2	Day 0	Medical visit/Rand	1.5 hr
Visit 3	Day 7	Core battery visit	45 min
Visit 4	Day 21	Core battery visit	45 min
Visit 5	Day 35	Core battery visit	45 min
Visit 6	Day 49	Medical visit	1.5 hr
Visit 7	Day 63	Core battery visit	45 min
Visit 8	Day 77	Core battery visit	1.5 hr
Visit 9	Day 91	Medical visit/EoT	1.5 hr
All	-	Total time at Center	12 hrs

Table 2. Summary of time required for the study participant.

Follow-up phone calls are scheduled at Day 7 and Day 30 after End-of-Treatment
Phone call Day+ 7: 15 min.

Phone call Day+ 30: 15 min

The total time required from the trial subject, including the phone calls, is 12.5 hrs.

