- Collect blood for laboratory tests: B-PEth, CDT and GGT analyses (Draw 15 ml blood)
- IMP distribution, collection of IMP kits from last visit and drug accountability by pill count

End of Analysis assessments

- Administer CPTA test via iPod
- Administer TEPS questionnaire
- Complete AUDIT
- Perform saliva dip stick test for cotinine analysis

Visit 9. End of Treatment/Medical visit. Accepted range +/- 3 days from schedules visit date

Medical examination by physician (30 min). AEs are collected as well as concomitant medication, vital signs and TLFB (data on alcohol consumption). Blood samples for alcohol specific outcome measures are drawn.

Core battery

- Complete TLFB alcohol calendar since last visit
- Administer VAS craving questionnaire
- Collect vital signs
- Collect AEs if any
- Record concomitant medication if any
- Collect blood for laboratory tests: B-PEth, CDT and GGT analyses (Draw 15 ml blood)
- Collection of IMP kits from last visit and drug accountability by pill count

End of Treatment and safety assessments

- Patient trial card collection
- Perform physical examination, which includes examination of armpits (lymph nodes), examination of mouth and throat, auscultation of heart and lungs, and palpitation of abdomen.
- Collect vital signs: Blood pressure, heart rate after 10 min rest, and weight (at visit 1 and visit 9)
- Draw blood for safety parameters, AST, ALT, PK, glucose, PK, creatinine, Na+/K+, Hb, LPK, TPK and hsCRP
- Perform drug of abuse test (U-tox)
- Administration of MADRS (safety endpoint)
- Complete DUDIT questionnaire (safety endpoint)

Follow-up Phone call (7 days after EoT)

Estimated time for phone call is 15 min.

- Collect/follow up AEs if any
- Record concomitant mediation if any
- Complete TLFB alcohol calendar data

Follow-up Phone call (30 days after EoT)

Estimated time for phone call is 15 min.

- Collect/follow up AEs if any
- Record concomitant mediation if any
- Complete TLFB alcohol calendar data for 7 days back in time

Extra study visits

If judged as required by the investigator, an extra study visit may be scheduled in addition to the ordinary study visits. The date, the reason for and the action taken at the visit must be documented in the CRF in a similar manner as for the pre-scheduled study visits. Additional blood (20 ml) will be drawn if judged as necessary.

Premature discontinuation

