In the case of premature study discontinuation, an End-of-Treatment visit will be performed. In addition, any outcome measures at the ordinary visit that are not covered by the End-of-treatment visit will be collected (applicable for visit 4,6 and 8) . Discontinued subjects will also complete an AE report by phone call Day 7+ and, if AEs persist, at Day +30 (see Section 4.4).

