4.4. Discontinuation and withdrawal of subjects

The participation in the clinical trial is voluntary and the subjects can decline further participation at any time without providing any motive for the discontinuation. They can also without any given reason at any time demand that their blood and urine samples are destroyed and that their randomization number is removed. If a subject discontinues or is withdrawn from the trial, EoT visit will be performed. In addition, any outcome measures at the ordinary visit that are not covered by the EoT visit will be collected (applicable for visit 4, 6 and 8). AEs will be followed by one (day +7), or if the AEs persists, by two phone calls (day +30).

Withdrawal of subject may take place due to:

- **Incorrect enrolment**

The exclusion criteria (Section 4.2.) apply during the entire study period. Based on the exclusion criteria, subjects will be excluded from the trial before the start of the trial and subjects may also be excluded from the trial and/or study drug during the whole study period

- **Protocol deviations**

The subjects may be withdrawn from the study at the discretion of the investigator if judged non-compliant with study procedures. Subjects will be excluded from the analysis set, if they are no longer judged to fulfill the eligibility criteria; e.g. if the subject has initiated a prohibited medication or other medication not listed or a non-pharmacological treatment considered to compromise the outcome measures in the study. A list of important protocol deviations will be finalized prior to study un-blinding. The number and percentages of

patients with at least one important protocol deviation will be summarized by treatment arm and overall. In addition, the number and percentages of patients within each type of protocol deviation will be provided as well, and a listing of all patients with any important protocol violations/deviations will be provided for the ITT population.

- **Safety Concerns**

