7.3. Reporting**7.3.1. Adverse Event (AE)**

All AEs occurring during the trial that are observed by study personell or reported by the subject, will be recorded by the study coordinator on the CRF, whether or not attributed to trial medication. All reported AEs will be judged and signed by responsible medical doctor. The following information will be recorded:

description, date of onset and end date, severity, assessment of relatedness to trial medication and action taken. Follow-up information should be provided as necessary.

The Investigator's clinical judgment will decide whether or not an AE is of sufficient severity to require the participant's removal from treatment. A subject may also voluntarily withdraw from treatment due to what he or she perceives as an intolerable AE. At pre-term termination due to AE, the participant must undergo an end-of-trial assessment and be given appropriate care under medical supervision until symptoms cease, or the condition becomes stable.

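### An early stopper with no adverse event ongoing at Day +7 has no scheduled AE contact for the next 23 days, whereas the general schedule includes an unconditional Day +30 call

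*Protocol*

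**What the plan says.** The general schedule attaches no condition to either call. Protocol Section 3.1 states: "Follow-up phone calls are scheduled at Day 7 and Day 30 after End-of-Treatment". Section 3.3 then lists a "Follow-up Phone call (30 days after EoT") among the standing procedures, and the AE item for both calls reads "Collect/follow up AEs if any", which covers new events as well as known ones.

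Subjects who stop early have their own rule. Under Premature discontinuation, Section 3.3 provides: "In the case of premature study discontinuation, an End-of-Treatment visit will be performed". It then adds: "Discontinued subjects will also complete an AE report by phone call Day 7+ and, if AEs persist, at Day +30". Section 4.4 gives the same rule for anyone who discontinues or is withdrawn: "AEs will be followed by one (day +7), or if the AEs persists, by two phone calls (day +30").

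Three provisions in Section 7.3 apply to all subjects. Section 7.3.1 sets the general recording rule, "All AEs occurring during the trial that are observed by study personell or reported by the subject, will be recorded", and for those who stop because of an AE it adds: "At pre-term termination due to AE, the participant must undergo an end-of-trial assessment", followed by supervised care until the symptoms cease or the condition is stable. Section 7.3.2 has drug-related AEs followed to resolution or stability. Section 7.3.3 requires SAEs to be reported within 24 hours of the site team becoming aware of them.

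**The concern.** The period after EoT in which subjects are actively asked about new events depends on whether they completed treatment and, for early stoppers, on whether an AE is still present at Day +7. The protocol gives no reason for the difference. An early stopper who is free of AEs at Day +7 is not asked again, while a completer in the same state is asked at Day +30.

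Two things are at stake. First, a new AE or SAE arising between Day +7 and Day +30 in such a subject reaches the database only through spontaneous report or chance. Second, Section 8.2 summarises safety by treatment group. If the share of subjects with the shorter window differs between arms, and post-treatment events enter those summaries, the arms will not have been observed equally.

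**Working it through.** There is no stated figure in the protocol to reproduce. The check is a comparison of the follow-up rules plus simple arithmetic.

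**Step 1: scheduled AE contact after EoT, by type of subject**

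| Subject | Day +7 call | Day +30 call | Window actively covered |
|---|---|---|---|
| Completer (Sections 3.1, 3.3) | yes | yes, collects new AEs | 30 days |
| Early stopper, AE persisting at Day +7 (3.3, 4.4) | yes | yes | 30 days |
| Early stopper, no AE persisting at Day +7 (3.3, 4.4) | yes | no | 7 days |

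The AE/SAE row of Table 1 carries 11 ticks, which fits nine visits plus two calls. The column alignment of that table is not reliable in the text available, so this is supporting evidence only.

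**Step 2: length of the gap**

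30 − 7 = 23 days; 23 / 30 = 0.77, i.e. 77% of the post-treatment window.

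**Step 3: does another provision close it?**

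- The recording rule in Section 7.3.1 is passive. It says what to do with an event that is observed or reported, but adds no contact.
- The care in Section 7.3.1 after stopping for an AE, and the follow-up in Section 7.3.2, concern the known event. Neither schedules a search for new ones, and neither applies to someone who stops for another reason without an AE.
- The 24-hour clock in Section 7.3.3 starts at site awareness, so it does not create awareness.

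The gap in the third row of the table therefore stands.

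**Step 4: how many subjects?**

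Section 8.1 gives 6.5% loss, but from randomization to the modified ITT set, not discontinuation during treatment. No on-treatment rate is stated. Purely as an assumption, 10% to 30% of the 380 randomized would be 0.10 × 380 = 38 to 0.30 × 380 = 114 early stoppers. Those with an AE persisting at Day +7 must be subtracted, and their number is unknown.

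**Step 5: can a difference between arms be quantified?**

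Let p be the proportion of an arm that stops early and q the proportion of those without a persisting AE at Day +7. The mean actively covered window is 30 − 23 × p × q days. Two illustrations use the same assumed stopping rates, 30% in the combination arm and 15% on placebo:

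- No early stopper has a persisting AE (q = 1 in both arms): 30 − 23 × 0.30 = 23.1 days against 30 − 23 × 0.15 = 26.55 days. The difference is 3.45 days, and 23.1 / 26.55 = 0.87, i.e. about 13% less on the combination.
- Two thirds of combination stoppers and one third of placebo stoppers have a persisting AE (q = 1/3 and 2/3): p × q = 0.30 × 1/3 = 0.10 and 0.15 × 2/3 = 0.10, so both arms average 30 − 2.3 = 27.7 days. The difference is zero.

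The same stopping rates give anything from a 13% deficit to none, depending on q. The quantity that matters is p × q by arm, and the protocol supplies neither factor.

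**The case against.** The strongest reply is that this is a deliberate rule, not a contradiction. Sections 3.3 and 4.4 agree with each other, and a specific rule for early stoppers can override a general schedule. Section 4.4 also lets subjects leave at any time without giving a reason, so lighter contact is coherent. This stands as far as it goes: the two rules can coexist. It does not explain why subjects who still accept a Day +7 call should not be asked again at Day +30.

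Three stronger readings are tempting, and the protocol does not support them.

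- A reader might infer that the gap falls mainly on people who stop for poor tolerability. They are the likeliest to have an AE persisting at Day +7, and so to receive the Day +30 call, and Section 7.3.1 adds supervised care for that AE. The gap falls on early stoppers who are AE-free at Day +7.
- A reader might infer that late events are lost, or that late SAEs go unreported. Events that the subject volunteers, or that the site otherwise discovers, must still be recorded, and SAEs reported. What is missing is active enquiry.
- A reader might infer that hypertension and depressive symptoms are monitored for 30 days in completers and 7 in early stoppers. The calls as listed in Section 3.3 comprise AEs, concomitant medication and TLFB, with no blood pressure or MADRS. Section 7.1 places blood pressure at study visits and post-baseline MADRS at visits 4 and 9, and early stoppers do get the EoT visit. After EoT, all subjects have self-report only for these risks.

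It is also fair to say that bias between arms is not shown. Safety analysis is descriptive, and the protocol does not say how events from the follow-up calls are tabulated, which may be left to the SAP.

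**Conclusion.** The point holds in a limited form. Early stoppers with no AE ongoing at Day +7 have no scheduled AE contact for 23 of the 30 days after EoT, while completers, and early stoppers with a persisting AE, are called at Day +30. This reads the +7 and +30 clock for early stoppers as starting at their EoT visit. The number of subjects affected cannot be computed from the protocol. A difference in ascertainment between arms is possible but not established: it would need the share of early stoppers without a persisting AE to differ by arm, and the illustrations above show that it can vanish even when stopping rates differ twofold. The primary analyses are not touched. This is an inexpensive improvement to safety follow-up, not evidence of a biased safety comparison.

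**What to change.** In Section 3.3 (Premature discontinuation) and Section 4.4, remove the condition on the Day +30 call. State that every subject who took at least one dose receives both the +7 and +30 calls, timed from EoT, each collecting new AEs and following up ongoing ones as for completers, unless the subject declines further contact. This makes the planned AE window independent of completion status and brings both sections into line with Section 3.1.

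The cost is a wording amendment and one additional 15-minute call per affected subject, using a procedure that sites already run. Some early stoppers will be unreachable or will decline, so coverage will improve without becoming complete.

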3.4. Study assessments

A summary of the study assessments in time is given in Table 1 in the Synopsis.

Investigator's training

The investigators and delegated qualified personnel will be trained in the study procedures, assessments and administration of scales required during the study. The training will be documented by a training certificate. The required scales and procedures for training are:

- Phone pre-screening
- The informed consent procedure
- Structured diagnostic interviewing
- The TLFB Alcohol procedure including interviewing technique
- Collection of AE and reporting of SAE
- Administration of study scales
- Handling of study specific medical device
- CPTA test administration on electronic device
- The electronic CRF system
- Study drug and randomization procedure
- Sampling, storing and sending procedure for blood analyses
- Procedure for study protocol violations and study drug non-compliance

Informed consent

Before enrolling the patient in the trial, i.e. before any trial-related examination is performed, Informed Consent must be obtained. Each potential participant will be informed, orally and in text, of the aim of the trial and what participation entails. They will be supplied with an Information Sheet summarizing the details of the trial. Ample time should be given to the patients to consider their participation. Agreement to participate in the trial is to be confirmed by the patient signing and dating the ICF. Documentation of this procedure is required. Documentation of the procedure is confirmed by the person who conducted the informed consent discussion signing and personally dating the ICF.

Breath alcohol concentration (BrAc)

BrAc will be measured at visit 1, to ensure sobriety during the informed consent and when performing the cognitive test (CPTA) and at visit 8, where CPTA is once again performed. BrAc is measured in exhaled air with a hand-held device, an Alcometer, and will provide an accurate estimate of the blood alcohol level. The Alcometer must be calibrated and documented, and used according the manufacturer's directions.

Demography

The demographic data that will be collected are: Gender and date of birth, civil status, number of children, and education. The age will be calculated in the eCRF.

AUD diagnosis

Documented diagnosis meeting ≥4 criteria according DSM-V by using structured interviewing.

Medical history

- History of previous psychiatric disorders, special attention to depression, previous suicidal attempts and other substance use disorders
- Previous and current medical conditions.
- History of alcohol dependence: familial cases of alcohol dependence, age of onset, mode(s) of alcoholisation, list of alcohol-use, CNS and somatic disorders, liver function tests, previous attempts of detoxification, alcohol consumption during the last month prior to inclusion. History of delirium tremens or abstinence-induced seizures
- Seizures, life time, alcohol-induced and non-alcohol-induced (see medical concerns section 1.3)
- Previous and current medication

Physical examination

A general physical examination including weight, examination of throat, armpits (lymph nodes), examination of mouth and throat, auscultation of heart and lungs, and palpitation of abdomen will be performed at the time points indicated above. Attention will be paid to abnormalities, which may have a bearing on the conduct of the trial (e.g., hypertension).

Vital Signs

The vital signs taken are blood pressure (systolic and diastolic) and heart rate and will be measured after 10 minutes of rest. The weight will be measured in kilograms with the patient lightly clothed but without shoes.

Clinical Laboratory parameters

Phosphatidylethanol in blood (B-PEth)

The direct alcohol marker PEth is found in red blood cells in humans in the presence of alcohol (Varga et al., 2000). The sensitivity of PEth is 94.5% and the specificity 100% (Hartmann et al., 2007), which is higher than for the commonly used alcohol markers CDT and GGT (Aradottir et al., 2006; Stewart et al., 2010; Hahn et al., 2012). The half-life of PEth is approx. one week, and the detection window days to several weeks (Wurst et al., 2010; Gnann et al., 2012; Hill-Kapturczak et al., 2018). There is no gender difference (Stewart et al., 2009) and liver disease has no influence on PEth levels (Stewart et al., 2009; Stewart et al., 2014). The positive correlation between PEth and alcohol intake has been established (Gnann et al., 2012; Stewart et al., 2014; Kechagias et al., 2015). PEth as a primary variable is shown to be superior to alcohol markers CDT and GGT (Walther et al., 2015) as well as self-reported alcohol intake (de Bejczy et al., 2015).

Carbohydrate-deficient transferrin (CDT)

CDT is a sensitive and specific indirect alcohol marker for recent moderate to heavy drinking. The iron-transporting protein transferrin is synthesized and secreted by the liver (Hashimoto et al. 2013) and the amount of the deficient isoforms of transferrin increases in response to heavy drinking. The exact amounts of alcohol required to elevate CDT are not known, although an intake of 50-80 g per day during 2-3 weeks probably is sufficient, at least in alcohol dependent individuals (Stibler 1991; Mikkelsen et al. 1998; Winkler et al. 2013). With a half-life reported in-between 7-16 days, the most reliable time frame of CDT is between 7-10 days (Hashimoto et al. 2013). As the methodology to measure CDT has not been standardized, the exact sensitivity and specificity of CDT is still not fully established (Helander et al. 1997). The sensitivity seems to be dose-dependent, with discrepancies in reported sensitivity as wide as 26 to 83 % (Hashimoto et al. 2013).

Gamma-glutamyl transferase (GGT)

GGT is a membrane-bound glycoprotein enzyme which increases in serum with chronic alcohol intake. Although widely used, the specificity and sensitivity of GGT vary in different studies. As in the case of CDT, the sensitivity of GGT seems to be dose-related (Aradottir et al. 2006). A daily alcohol intake of 80-200 g for several weeks is needed to detect activity of GGT in blood (Winkler et al. 2013). GGT has a half-life of approx. 4 weeks (Hashimoto et al. 2013) and increased activity returns to normal in 2-5 weeks after discontinued alcohol intake (Niemela 2007; Winkler et al. 2013).

*Scales and questionnaires***Adult ADHD self-report scale (ASRS)**

Eligibility measurement. The ASRS is a symptom checklist to help screen for ADHD in adult patients (Kessler et al., 2005). The questions in the ASRS v1.1 are consistent with DSM-IV criteria and address the manifestations of ADHD symptoms during the previous six months in adults. The checklist takes about five minutes to complete. For Swedish validated version of the ASRS scale, see Attachment 1.

Alcohol Use Disorders Identification Test (AUDIT)

Outcome measurement. AUDIT is a validated 10-item self-report scale developed by the World Health Organization to assess alcohol consumption, drinking behaviors and alcohol-related problems (Bohn et al., 1995; Babor TF, 2001). AUDIT was developed as a simple method of screening for excessive drinking and to assist in brief assessment. The AUDIT has been validated across genders and in a wide range of racial/ethnic groups. For Swedish validated version of the AUDIT scale, see Attachment 2.

Drug Use Disorder Identification Test (DUDIT)

Eligibility and safety measurement. DUDIT is a psychometric 11-item self-report questionnaire focusing on current drug-related problems (Berman et al., 2005). The DUDIT screens effectively for drug-related problems. The final 11 items in the DUDIT were chosen to give information on the level of drug intake and fulfilment of selected criteria for substance abuse/harmful use and dependence according to the ICD-10 and DSM-4 diagnostic systems. The DUDIT was developed and tested in Sweden, with the intention of expanding trials in Europe and elsewhere. For Swedish validated version of the DUDIT scale, see Attachments.

Montgomery-Asberg Depression Scale (MADRS)

Eligibility and safety measurement. MADRS is a validated 10-item self-rating scale for depressive symptoms and will be used as safety measure to monitor tentative changes in depressive status (Montgomery and Asberg, 1979). The included items are apparent sadness, reported sadness, inner tension, reduced sleep, reduced appetite, concentration difficulties, lassitude, inability to feel, pessimistic thoughts and suicidal thoughts. For Swedish validated version of the MADRS scale, see Attachments.

Temporal experience of pleasure scale (TEPS)

Outcome measurement. Anhedonia is a key feature of depression and negative symptoms of schizophrenia and is associated with social functioning in these patients. Anhedonia refers to the loss of or a reduction of the ability to experience pleasure. The temporal experience of pleasure scale (TEPS) is a 17-item scale with anticipatory and consummatory components of the experience of pleasure (Li et al., 2018) and is validated in a german population (Martinotti; et al.;Simon et al., 2017). TEPS will be used in the trial as a proxy to assess the hypodopaminergic (ventral striatum) hypotheses of AUD. For Swedish validated version of the TEPS scale, see Attachments.

Timeline Followback (TLFB)

Outcome measurement. The TLFB is a validated technique for assessing self-reported alcohol consumption. The drinking assessment method has been evaluated with clinical and non-clinical populations (Sobell and Sobell, 1992). People provide retrospective estimates of their daily drinking over a specified time period that can vary up to 12 months from the interview date. Several memory aids can be used to enhance recall e.g., calendar; key dates serve as anchors for reporting drinking; standard drink conversion. At screening, the subject will, together with the site staff, complete TLFB retrospectively for a period of 30 days before the visit. At every visit, the subject will complete the TLFB calendar covering the period between two following visits. The records will be checked and documented by the Investigator at each visit. The alcohol consumption will be quantified by collecting type of alcoholic beverage, volume percentage (% v/v) of alcohol and amount (e.g cl or ml) of beverage and converted into of pure alcohol in grams. For Swedish validated version of the TLFB calender, see Attachments.

VAS Craving

Outcome measurement. This is a single item instrument used to assess craving for alcohol and has previously been used in clinical trials. The alcohol craving is quantified via the Visual Analogue Scale, or VAS (Aitken, 1969). The VAS Craving Scale will not be administered via eCRF as the VAS scale is developed as a pencil-and-paper self-administration tool. A paper copy will be the source document. The Craving scale entails one question only. For Swedish version of the VAS Craving scale, see Attachments.

Continuous Performance Test + Activity (CPTA)

Outcome measurement. Opatus® CPTA is a neuropsychiatric tool that addresses the three entities inattention, impulsivity and activity (www.opatus.se). The test is presented on a mobile unit. Various symbols are flashed on to the screen and the task is to respond, by tapping the screen, to certain symbols (targets), and to not respond to other symbols (non-targets), as quick and accurate as possible. Although a simple task, its limited amusement factor makes it difficult for some to keep up the attention causing erratic responses to be more frequent. Hyperactivity is one of the core symptoms of ADHD. The CPTA utilizes built-in accelerometers and gyros in the smartphones to assess motor activity level. *Attention:* Opatus CPTA monitors how often presented targets are not responded on and how consistent correct responses are in time. *Impulsivity:* Opatus CPTA monitors how often responses are registered when no targets are present, how often responses are so quick (<150 ms) they are considered guesses rather than responses, or multiple responses to one symbol. *Activity:* Opatus CPTA records how the mobile has been moved around in the 3D space during the test. The test is administrated via a mobile unit (iPod). Test time: 20 minutes. Opatus CPTA will be used in the trial as a proxy to assess the hypofrontality/hypodopaminergic (frontal cortex) hypothesis of AUD.

Clinical Laboratory parameters

Eligibility, safety and outcome measurements. Appointed by the coordinating center, a central laboratory will analyze B-PEth from all study sites. Safety parameters and secondary outcome measures will be analyzed at the Investigator's site according to common practice. The Investigator at each study center will review and evaluate the results of the blood and urine safety analysis samples obtained at the screening visit to determine the patient's eligibility. The laboratory variables that will be determined are listed in Table 3. Before the patient is allowed to enter the study, clinical laboratory blood and urine tests will be performed and the absence of clinically significant abnormalities will be confirmed by the Investigator. The time of blood sampling will be recorded in the laboratory requisition form and transferred to the eCRF. A laboratory manual with detailed information regarding sample collection, handling, and labeling will be available at each study site.

Alcohol markers	Hematology	Biochemistry	Urinalysis	Saliva analysis
Phosphatidylethanol (At each visit)	Hemoglobin (v1, v9)	Aspartate Aminotransferase, Alanine Aminotransferase	Women Human chorionic gonadotropin (v1, v2, v9)	Cotinine (v2, v8)
Carbohydrate deficient transferrin (At each visit)	Leukocyte plasma count (v1, v9) Thrombocyte particle concentration	(v1, v4, v9) Glucose (v1 and v9)		
Gammaglutamyl- Transferas			All	

(At each visit) In exhaled air BrAC (v1, v8)	(v1, v9)	Na+/K+ (v1 and v9) High sensitive C-reactive protein (v1, v9) Creatinine (v1, v4, v9) Prothrombin Complex (v1, v4, v9)	Drug of abuse (toxicology) (v1,v2 v9)	Pharmaco. kinetic Drug (BUP, VAR) plasma concentrations (v4, v6) **
--	----------	---	---------------------------------------	---

Table 3. List of Clinical laboratory parameters that will be analyzed in the trial

* Amphetamines/Methamphetamine, Barbiturates, Benzodiazepines, Cannabinoids, Cocaine, Ecstasy, Heroin, Opiates, Methadone, Tricyclic Antidepressants ** To be determined/analysed after study database closure to maintain double-blind condition

